3.8 COST AND COMPENSATION

3.8.1 Costs

NIH does not bill health insurance companies or participants for any research or related clinical care that participants received at the NIH Clinical Center. If some tests and procedures are performed outside the NIH Clinical Center, participants may have to pay for these costs if they are not covered by insurance company. Medications that are not part of this study will not be provided or paid for by the NIH Clinical Center.

3.8.2 Compensation

There will be no compensation provided in this study.

3.8.3 Reimbursement

The NCI will cover the costs of some expenses associated with protocol participation. Some of these costs may be paid directly by the NIH and some may be reimbursed to the participant/guardian as appropriate. The amount and form of these payments are determined by the NCI Travel and Lodging Reimbursement Policy.

3.9 CRITERIA FOR REMOVAL FROM PROTOCOL THERAPY AND OFF STUDY CRITERIA

Prior to removal from study, effort must be made to have all subjects complete a safety visit approximately 28 days after the last dose of study therapy. Additional visits and follow up will continue as per Section [3.7](#). Participants who refuse to return for this visit will be asked to review any safety concerns by phone within this time period.

3.9.1 Criteria for removal from protocol therapy

- Participant requests to be withdrawn from active therapy.
- Unacceptable Toxicity as defined in Section [3.4.1](#) that require treatment discontinuation.
- Completion of treatment.
- **Disease Progression:** Clinical or radiographic progression of disease, except where per investigator clinically appropriate and the participant is achieving clinically meaningful benefit from treatment with bintrafusp alfa (See also Section [3.9.1.1](#)).
- Intercurrent illness that prevents further administration of the treatment.
- Start of another systemic anticancer treatment or participation in another investigational therapeutic trial. Focal palliative radiotherapy, ablation, or surgery to a site of disease will not necessitate removal from protocol therapy.
- Investigator discretion.
- Non-compliance with study treatment or procedure requirements.
- Positive pregnancy test.
- Study is cancelled for any reason.
- Permanent loss of capacity to give consent.

Participants who are off-treatment but still on-study will have remaining study procedures completed as indicated by the study protocol.

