2.1.2 Exclusion Criteria

2.1.2.1 Anticancer treatment, concurrent or prior (chemotherapy, monoclonal antibody, cytokine therapy, immune therapy, targeted small molecule therapy) or any

investigational drug, within 4 weeks or 5 half-lives (whichever shorter) prior to the first drug administration. All residual treatment-related toxicities must have resolved or be minimal and not constitute a safety risk. **Note:** Palliative radiotherapy is permitted concurrently or within the pretreatment period. Subjects receiving bisphosphonates or denosumab are eligible provided treatment was initiated at least 14 days before treatment.

- 2.1.2.2 Participants who received prior checkpoint blockade therapy and were taken off treatment for serious adverse events related to immuno-therapy are excluded.
- 2.1.2.3 Major surgery within 4 weeks prior to the first drug administration (minimally invasive procedures such as diagnostic biopsies are permitted).
- 2.1.2.4 Active or prior documented autoimmune or inflammatory diseases that might deteriorate on immunostimulatory agent (including colitis or Crohn's disease, systemic lupus erythematosus, sarcoidosis, vasculitis, Grave's disease, hypophysitis, uveitis, rheumatoid arthritis etc.), **except** the following:
 - Type I diabetes mellitus
 - Chronic skin conditions that do not require systemic therapy (including eczema, vitiligo, alopecia, psoriasis)
 - Hypothyroidism (e.g., post-Hashimoto thyroiditis) stable, on hormone replacement
 - Mild autoimmune disease not active in the last 5 years may be eligible after consultation with the principal investigator.
- 2.1.2.5 Current use of immunosuppressive medication within 14 days before the first dose of the study medication, **except** the following:
 - Intranasal, inhaled, topical glucocorticoids; locally injected glucocorticoids (i.e. intra-articular, intra-ocular)
 - Systemic glucocorticoids at physiologic doses (generally \leq 10 mg prednisone or equivalent per day)
 - Glucocorticoids as premedication for contrast-enhanced studies is allowed prior to enrollment and on study.
- 2.1.2.6 Uncontrolled intercurrent chronic or acute illness including, but not limited to the following, that may limit interpretation of results or increase risk to the participant in the judgment of the investigator:
 - Bleeding diathesis or recent (<3 months) clinically significant bleeding event.
 - Prior organ transplantation including allogenic stem-cell transplantation

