6. Subsequent Post-treatment follow-up: Every 3 months (+/- 2 weeks), starting after the safety visit for the first year, followed by every 6 months (+/- 4 weeks) for years 2-5, and then annually (+/- 6 weeks) thereafter at the discretion of the investigator. Follow-ups may be done by phone/email or by clinic visit at the discretion of the investigator. Follow-up via telephone/email will include survival, adverse events, and assessment of further tumor therapy; furthermore, routine outside blood, urine, and imaging results may be collected and used for analysis at the discretion of the investigator. Any other evaluations and tests should be performed as clinically indicated. Participants who have not progressed on treatment will be scanned until progression. Those that completed the previous 26-doses course and have progression will be invited for an additional course (26 doses) at the time of progression.
7. Bintrafusp alfa administered IV at flat dose of 1,200 mg.
8. As indicated in Section **12.3**, all subjects will be offered the opportunity to complete an NIH advance directive form. This should be done preferably at baseline but can be done at any time during the study as long as the capacity to do so is retained. The completion of the form is strongly recommended but is not required.
9. Every 6 weeks.
10. Imaging (Section **6.3**) will be performed every 8 weeks (+/- 1 week). In the event of a PR or CR, tumor imaging assessments may be performed every 3 months (+/- 2 weeks) at the discretion of the investigator. Tumor assessment should be continued beyond end of treatment in participants who have not experienced PD until they experience PD in order to assess PFS. Additional imaging to be performed at the investigator's discretion. Imaging performed in outside facilities maybe utilized in the case of travel restrictions or delays, airport closures, inclement weather, family responsibilities, security alerts and government holidays, etc. Nuclear bone scan or imaging may be done for individuals with known/suspected bone lesions at screening; in these cases bone scans should be done in follow-up for response assessments.
11. Optional biopsies: at baseline (within 2 weeks prior to first treatment) and within 2 weeks of first imaging restaging; optional biopsy at/near progression, where clinically feasible.

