4.1 ACCEPTABLE MEDICATIONS/MEASURES

All routine and appropriate treatments and supportive care (including blood products) that the investigator considers necessary for a participant's welfare or symptom alleviation may be administered at the discretion of the investigator in keeping with the community standards of medical care.

Palliative radiotherapy to non-targeted lesions delivered in a normal organ-sparing technique may be administered during the trial. The assessment of PD will not be based on the necessity for palliative radiotherapy.

Traditional herbal or homeopathic or natural medicines should be **avoided**. Ingredients for such medicines have not been fully studied, and their use may result in unanticipated drug-drug interactions that may cause toxicity or confound assessment of toxicity. Herbal medications include, but are not limited to St. John's Wort, kava, ephedra, gingko biloba, yohimbe, saw palmetto, black cohosh, ginseng, turmeric, and curcumin.

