6.3.4 Evaluation of Best Overall Response

The best overall response is the best response recorded from the start of the treatment until disease progression/recurrence (taking as reference for progressive disease the smallest measurements recorded since the treatment started). The participant’s best response assignment will depend on the achievement of both measurement and confirmation criteria (See [Appendix C](#): Best Overall Response per RECIST 1.1).

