10.2 SAMPLE SIZE DETERMINATION

There is no published literature on the anticipated efficacy of any specific treatment for participants with ONB. In these rare participants, the objective will be to determine if a modest response rate is possible while keeping the study size small. Thus, in immune checkpoint-naïve participants, this trial will be conducted using a Simon optimal two-stage phase II trial design (Simon R, Controlled Clinical Trials 10:1-10, 1989) to rule out an unacceptably low response rate (CR+PR) of 5% ($p_0=0.05$) in favor of an improved response rate of 20% ($p_1=0.20$). With $\alpha=0.10$ (one sided alpha; equals two-sided alpha = 0.20; probability of accepting a poor treatment=0.10) and $\beta=0.20$ (probability of rejecting a good treatment=0.20), the first stage will enroll 12 evaluable participants, and if 0 of the 12 has a response, then no further participants will be accrued. If 1 or more of the first 12 participants has a response, then accrual would continue until a total of 21 evaluable participants have been treated. As it may take up to several months to determine if a participant has experienced a response, a temporary pause in the accrual may be necessary to ensure that enrollment to the second stage is warranted. If there are 1-2 participants with a response out of 21 participants, this would likely be an uninterestingly low response rate. If there were 3 or more of 21 (14.3%) who experienced a response, this would be sufficiently interesting to warrant further study in later trials. Even if there are fewer than 3 responses, this will provide information on degree of efficacy of a single agent in a rare disease where there is currently no published

information. Under the null hypothesis (5% response rate), the probability of early termination is 54.0%.

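### Best overall response has no cut-off at surgery or ablation of a target lesion, or at a new systemic treatment started before progression, so shrinkage not caused by the study drug can enter the primary endpoint

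*Combined protocol and SAP*

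**What the plan says.** All references are to the combined protocol and SAP.

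- **Local treatment on study.** Section 3.9.1: "Focal palliative radiotherapy, ablation, or surgery to a site of disease will not necessitate removal from protocol therapy". Target lesions are not excluded. Section 4.1 is narrower, for radiotherapy only: "Palliative radiotherapy to non-targeted lesions delivered in a normal organ-sparing technique may be administered during the trial". The note to exclusion criterion 2.1.2.1 has no lesion limit: "Palliative radiotherapy is permitted concurrently or within the pretreatment period". No section sets a lesion limit for surgery or ablation.
- **Other systemic treatment.** Section 4.2 prohibits it during the trial, and section 3.9.1 ends protocol therapy when it begins. Participants off treatment can stay on study for the remaining procedures.
- **Response window.** Section 6.3.4: "The best overall response is the best response recorded from the start of the treatment until disease progression/recurrence". Section 6.3 adds that every image taken while the trial runs is considered.
- **Scans after treatment.** Footnote 10 to the study calendar (3.7): "Tumor assessment should be continued beyond end of treatment in participants who have not experienced PD", with PFS given as the purpose. Footnote 6 has further tumour therapy recorded at remote follow-up.
- **Scoring.** Section 6.3.3.1 defines target-lesion CR and PR by lesion size alone. Sections 10.3.2 (evaluability) and 10.4.1 (primary analysis) and Appendix C do not say how to score a treated target lesion, and do not stop the count at new therapy.

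**The concern.** The primary endpoint is the response rate to bintrafusp alfa in a single-arm trial, so no control group absorbs responses that have another cause. Two routes are open.

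1. A target lesion is resected or ablated while the participant stays on protocol therapy. The lesion then measures zero, or smaller, at the next scan.
2. A participant stops study drug without progression (for toxicity or by choice, say), starts another systemic drug, is still being scanned, and shrinks by 30% or more before PD.

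Confirmation at four weeks or later does not close the first route, because a resected lesion is still absent on the repeat scan. The thresholds are very low: one response in 12 opens stage 2, and three in 21 is the mark for further study. A single misattributed response can decide either.

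**Working it through.** **How easily local treatment meets the size criteria.** PR needs a fall of at least 30% in the sum of diameters. Suppose a participant has k target lesions of equal size, one is removed and scored as zero, and the others do not change. The sum then falls by 1/k: 100% for k = 1, 50% for k = 2, 33.3% for k = 3 and 25% for k = 4. Eligibility needs only one measurable lesion, so with one to three equal lesions a single procedure reaches the PR threshold for target lesions.

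**Inputs (section 10.2).** The design is meant to "rule out an unacceptably low response rate (CR+PR) of 5" per cent (p0 = 0.05) in favour of 20% (p1 = 0.20). Alpha is 0.10 ("one sided alpha; equals two-sided alpha = 0.20; probability of accepting a poor treatment=0.10") and beta is 0.20 ("probability of rejecting a good treatment=0.20"). Stop if 0 of 12 respond; otherwise go to 21. Three or more of 21 is success.

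**Reproducing the plan's figures.** X(n) is the number of responses among n participants.

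- Early termination at 5%: 0.95^12 = 0.5404. The plan states 54.0%.
- P(success) = P(X(21) ≥ 3) − P(X(12) = 0) × P(X(9) ≥ 3).
- At 5%: 0.0849 − 0.5404 × 0.0084 = 0.0804, within the 0.10 limit.
- At 20%: 0.8213 − 0.0687 × 0.2618 = 0.8033, which meets 80% power.

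**Exactly one false response, true rate 5% in the other 20.**

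- In stage 1: stage 2 opens with certainty, instead of with probability 1 − 0.5404 = 0.4596. Success then needs two or more true responses among 20: 1 − 0.95^20 − 20 × 0.05 × 0.95^19 = 1 − 0.3585 − 0.3774 = 0.264.
- In stage 2: at least one true response is still needed in the first 12, and at least two among 12 + 8. That is 0.2642 − 0.5404 × P(X(8) ≥ 2) = 0.2642 − 0.5404 × 0.0572 = 0.233.

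**A false-response rate f among true non-responders (assumed).** The apparent response rate is p = 0.05 + 0.95f, put into the same two-stage formula.

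| f (assumed) | apparent rate p | P(success), true rate 5% |
|---|---|---|
| 0 | 0.0500 | 0.080 |
| 1% | 0.0595 | 0.120 |
| 2% | 0.0690 | 0.165 |
| 5% | 0.0975 | 0.322 |

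**Effect on the reported result.** One extra response moves 2/21 (9.5%, exact 95% CI 1.2% to 30.4%) to 3/21 (14.3%, CI 3.0% to 36.3%), which crosses the decision line.

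**The case against.** A reader might infer that any local treatment and any later drug can feed the response count without limit. The documents do not support that.

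- **Radiotherapy.** Section 4.1, which deals with permitted measures, confines on-trial palliative radiotherapy to non-targeted lesions. Criterion 2.1.1.2 lets an irradiated lesion serve as a target only if it has since progressed. Section 3.9.1 says what does not force removal from therapy; it does not itself permit irradiation of a target lesion. This largely stands. What is left is that 2.1.2.1 and 3.9.1 carry no matching limit.
- **Later drugs.** The window in 6.3.4 closes at progression, so a response to a drug started after PD does not count. This stands. The drug route is confined to participants who leave study drug without PD.
- **Intent.** Section 1.1.1 defines the endpoint as response to bintrafusp alfa, and post-treatment scans are there for PFS. That shows what was meant. But 6.3 brings in every image and the size criteria ignore cause, so the intent is not turned into a rule.
- **RECIST 1.1.** The plan defers to that guideline, which is not among the documents, so whether it covers treated lesions cannot be settled here. The criteria that the protocol writes out contain no such rule.
- **Frequency.** Participants must have disease not amenable to potentially curative local treatment, and the documents give no rate of on-study surgery or ablation. Few may be affected. This stands, and it limits what the calculations can show.

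**Conclusion.** The gap is real but narrow. It covers surgery or ablation of a target lesion at any time before PD, and a new systemic treatment started before PD by someone who stopped study drug without progression. In both cases the plan as written can score the result as CR or PR in the primary endpoint.

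The figures show how fragile a 1/12 then 3/21 rule is; they do not estimate how often misattribution will happen. The 26.4% and 23.3% take one false response as certain. The 12.0%, 16.5% and 32.2% rest on assumed rates that apply equally and independently to every non-responder. With that caveat, even an assumed 1% takes the false-positive probability past the planned 10%. The rule should be written before the data are analysed; the design itself does not need to change.

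**What to change.** State in sections 6.3.4 and 10.4.1, with the same rule for the stage 1 count in 10.4.5:

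1. Only assessments before the first local treatment of a target lesion, and before the first new systemic anticancer treatment, count towards CR or PR.
2. A participant without a qualifying response by then is a non-responder and stays in the denominator.
3. How to treat an initial response whose confirmation scan falls after the intervention. One workable choice is to leave it out of the primary count and add a sensitivity analysis that counts initial responses seen before the intervention.
4. How the sum of diameters, and the smallest sum used to judge PD, are calculated once a target lesion has been treated.

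Separately, reconcile the wording on local treatment in 2.1.2.1, 3.9.1 and 4.1. Which clinical rule should apply is for the sponsor to decide.

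The cost is a few sentences. No participants or procedures are added, further tumour therapy is already recorded at follow-up, and the 0/12 then 3/21 design keeps its 8.0% type I error and 80.3% power. The drawback is that a few genuine late responses may be lost, so the ORR may be slightly lower. At a threshold of three, one lost true response matters as much as one false one, which is why the sensitivity analysis in item 3 is needed.

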3.9.1.1 Treatment Beyond Progression

Response patterns to immunotherapy have included observations of clinical response after initial increases in tumor burden (termed “pseudo-progression”). Consequently, it is preferable that where clinically appropriate, participants remain on treatment past initial radiographic progression until disease progression is confirmed by subsequent imaging, 4 to 6 weeks (preferably 6 weeks but not later) after progression has been determined per RECIST1.1. (1) If progression is based on the occurrence of a new lesion in an area not scanned at Baseline, a further on-study scan 6 weeks later should be considered before performing the 28-day Safety follow-up visit. Clinically appropriate context entails the following:

- There are no new or concerning symptoms.
- There is no decline in ECOG PS.
- The Investigator does not consider it necessary to administer urgent salvage medical intervention.

3.9.2 Off-Study Criteria

- Participant requests to be withdrawn from study.
- Screen failure.
- Participant lost to follow up.
- Death.
- Investigator discretion.
- Study is cancelled for any reason.

3.9.3 Lost to Follow-up

A participant will be considered lost to follow-up if he or she fails to return for 4 consecutive scheduled visits and is unable to be contacted by the study site staff.

The following actions must be taken if a participant fails to return to the clinic for a required study visit:

- The site will attempt to contact the participant and reschedule the missed visit within 4 weeks and counsel the participant on the importance of maintaining the assigned visit schedule and ascertain if the participant wishes to and/or should continue in the study.
- Before a participant is deemed lost to follow-up, the investigator or designee will make every effort to regain contact with the participant (where possible, 3 telephone calls and, if necessary, an IRB approved certified letter to the participant’s last known mailing address or local equivalent methods). These contact attempts should be documented in the participant’s medical record or study file.
- Should the participant continue to be unreachable, he or she will be considered to have withdrawn from the study with a primary reason of lost to follow-up.

3.9.4 Trial discontinuation

- Evidence of inefficacy of the investigational drug (evidence of inefficacy may arise from this trial or from other trials).
- Occurrence of significant previously unknown adverse reactions or unexpected intensity or incidence of known adverse reaction (unfavorable safety findings may arise from clinical or non-clinical examinations, e.g., toxicology).
- Sponsor decision that continuation of trial is unjustifiable for medical or ethical reasons.
- Poor enrollment of participants, making completion of trial unlikely within acceptable time frame.
- Discontinuation of development of the investigational drug.
- Termination or suspension upon request of health authorities.

4 CONCOMITANT MEDICATIONS/MEASURES

Subjects must be instructed to inform the investigators of the current or planned use or all other medications during the study (including prescription medications, over-the-counter medications, vitamins and herbal and nutritional supplements).

For this protocol, a prescription medication is defined as a medication that can be prescribed only by a properly authorized/licensed clinician. Medications to be reported in the Case Report Form (CRF) are concomitant prescription medications, over the counter (OTC) medications, herbal supplements, and IV medications and fluids. If changes occur during the trial period, documentation of drug dosage, frequency, route, and date may also be included on the CRF. All concomitant medications received starting from 30 days prior to the first dose of trial treatment and 30 days after the last dose of trial treatment should be recorded.

4.1 ACCEPTABLE MEDICATIONS/MEASURES

All routine and appropriate treatments and supportive care (including blood products) that the investigator considers necessary for a participant's welfare or symptom alleviation may be administered at the discretion of the investigator in keeping with the community standards of medical care.

Palliative radiotherapy to non-targeted lesions delivered in a normal organ-sparing technique may be administered during the trial. The assessment of PD will not be based on the necessity for palliative radiotherapy.

Traditional herbal or homeopathic or natural medicines should be **avoided**. Ingredients for such medicines have not been fully studied, and their use may result in unanticipated drug-drug interactions that may cause toxicity or confound assessment of toxicity. Herbal medications include, but are not limited to St. John's Wort, kava, ephedra, gingko biloba, yohimbe, saw palmetto, black cohosh, ginseng, turmeric, and curcumin.

